5.1. Analysis Principles

Statistical analysis will be conducted after database is locked and performed using SAS software version 9.4 or higher according to this statistical analysis plan (SAP). If statistical analysis methods are changed, it will be described in the final clinical study report.

Continuous variables will be summarized by the descriptive statistics (number (n), mean, standard deviation (SD), median, minimum and maximum). Categorical variables will be presented in frequency and percentage (with the percentage excluding the number missing in the denominator).

In case of statistical hypothesis testing, two-sided tests will be conducted at a 5% significance level and the p-value of each test result will be presented in the summary table.

Statistical Analysis Plan for rPMS

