### **3.9.2. Interim Analysis**

As required by MFDS regulations, the periodic report should be submitted to MFDS every 6 months for the first two years and then annual report should be submitted to MFDS for the third, fourth and fifth year. The final report for the date collected until August 21, 2018 should be submitted in the sixth year, by November 21, 2018. For the additional study period, periodic report should be submitted to MFDS every 6 months, and the final report of the entire study period should be submitted by November 21, 2021. Interim analysis will be performed in time for the report submission.

Analysis will be performed for safety group and efficacy group for patients who are prescribed with INLYTA® for the first time and for patients who are already on INLYTA® separately, and for all enrolled patients.

- Safety group: Subjects who have been administered INLYTA® at least once and evaluated with safety-related endpoints at least once.
- Efficacy group:ITT (Intent-to-treat) group - subjects to whom INLYTA® is administered INLYTA® at least once.

Detailed methodology for summary and statistical analyses of data collected in this study will be documented in a Statistical Analysis Plan (SAP), which will be dated, filed and maintained by the sponsor. The SAP may modify the plans outlined in the protocol; any major modifications of primary endpoint definitions or their analyses would be reflected in a protocol amendment.

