 - Discontinuation (permanently, temporarily or delayed)
 - Dosage reduced
 - Dosage increased
 - No change
 - Unknown
 - Not applicable
- 3) Occurrence status of adverse events by demographic and other baseline characteristics
 - The incidence of adverse events and 95% CI will be presented by categorical variables of demographic and other baseline characteristics.
 - To identify statistically significant difference in incidence of adverse events by categorical variables of demographic and other baseline characteristics, Chi-square test (χ^2 test) or Fisher's exact test (if the expected frequency for each cell under 5 is more than 20%) will be performed.
- 4) Analysis of factors that affect the safety
 - In the re-examination report, logistic regression or multivariate analysis will be performed and an odds ratio with 95% CI and p-value will be presented to identify the factors that affect incidence of adverse events in demographic and other baseline characteristics.
- 5) Analysis for special patient populations [pediatric subjects (aged < 19 years), geriatric subjects (aged \geq 65 years), subjects with renal impairment, subjects with hepatic impairment]
 - Adverse events and adverse drug reactions collected in each special patient population will be presented the number of subjects having adverse events, incidence of adverse events and the number of adverse events for each SOC and PT.
- 6) Analysis for population except from safety analysis
 - Adverse events and adverse drug reactions collected in population except from safety analysis will be presented the number of subjects having adverse events, incidence of adverse events and the number of adverse events for each SOC and PT.

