6.3. Efficacy Analyses

Efficacy analyses will be performed based on data of efficacy analysis set.

- 1) Best overall response [Complete response (CR), Partial response (PR), Stable disease (SD), Progressive disease (PD), Not evaluable (NE)] will be presented in frequency and percentage.
- 2) Objective response rate (ORR) will be presented in frequency and percentage.

Objective response rate (ORR)

$$= \frac{\text{Number of subjects who achieves a best overall response of CR or PR}}{\text{Number of subjects in the efficacy analysis set}}$$

Statistical Analysis Plan for rPMS

- 3) Kaplan-Meier curve for time-to-event endpoints will be generated and presented quartiles with 95% CI, event rates and censor rates. Date of death is date of resolution of serious adverse event in which the category of seriousness is 'Results in death'. In case subjects do not have an event, censor of time-to-event is performed at the date of final follow-up.
 - Progression-free survival (PFS)
 - Time to progression (TTP)
- 4) Objective response rate (ORR) by demographic and other baseline characteristics
 - Objective response rate and 95% CI will be presented by categorical variables of demographic and other baseline characteristics.
 - To identify statistically significant difference in objective response rate by categorical variables of demographic and other baseline characteristics, Chi-square test (χ^2 test) or Fisher's exact test (if the expected frequency for each cell under 5 is more than 20%) will be performed.
- 5) Analysis of factors that affect the efficacy
 - In the re-examination report, logistic regression or multivariate analysis will be performed and an odds ratio with 95% CI and p-value will be presented to identify the factors that affect objective response rate in demographic and other baseline characteristics.

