[Table 22] Adverse events by action	18
[Table 23] Occurrence status of adverse events by demographic characteristics	19
[Table 24] Occurrence status of adverse events by other baseline characteristics.....	19
[Table 25] Multivariate logistic regression for occurrence status of adverse events	21
[Table 26] Best overall response and objective response rate	21
[Table 27] Summary statistics for progression-free survival	22
[Table 28] Summary statistics for time to progression.....	23
[Table 29] Objective response rate by demographic characteristics	24
[Table 30] Objective response rate by demographic and other baseline characteristics	24
[Table 31] Multivariate logistic regression for objective response rate	26
[Table 32] Adverse events and adverse drug reactions of pediatric subjects (aged < 19) (N=xxx)	27
[Table 33] Adverse events and adverse drug reactions of geriatric subjects (aged ≥ 65) (N=xxx)	27
[Table 34] Adverse events and adverse drug reactions in the subjects with renal impairment (N=xxx)	27

Dummy Table

[Table 35] Adverse events and adverse drug reactions in the subjects with hepatic impairment (N=xxx)	27
[Table 36] Reasons for excluding safety evaluation (N=xxx).....	28
[Table 37] Adverse events and adverse drug reactions in the subjects excluded from safety analysis (N=xxx).....	28

LIST OF FIGURE

[Figure 1] Kaplan-Meier curve for progression-free survival	22
[Figure 2] Kaplan-Meier curve for time to progression	23

Dummy Table

[Table 1] Demographic characteristics

Factor	Classification	Number of subjects n(%)
Sex	Male	xxx(xx.xx)
	Female	xxx(xx.xx)
	Total	xxx(xx.xx)
Age (year)	n	xxx
	Mean±SD	xx.xx±xx.xx
	Median	xx.xx
	Min~Max	xx.xx~xx.xx
	Category 1	xxx(xx.xx)
	Category 2	xxx(xx.xx)
	Category 3	xxx(xx.xx)
	...	xxx(xx.xx)
	Total	xxx(xx.xx)
Pediatric	< 19 years	xxx(xx.xx)
	≥ 19 years	xxx(xx.xx)
	Total	xxx(xx.xx)
Geriatric	≥ 65 years	xxx(xx.xx)
	< 65 years	xxx(xx.xx)
	Total	xxx(xx.xx)
Classification	Outpatient	xxx(xx.xx)
	Inpatient	xxx(xx.xx)
	Total	xxx(xx.xx)
Height (cm)	n	xxx
	Mean±SD	xx.xx±xx.xx
	Median	xx.xx
	Min~Max	xx.xx~xx.xx
Weight (kg)	n	xxx
	Mean±SD	xx.xx±xx.xx
	Median	xx.xx
	Min~Max	xx.xx~xx.xx

[†]Number of missing

Programming note: The categories of age will be set considering distribution of data.

[Table 2] Other baseline characteristics

Factor	Classification	Number of subjects n(%)
Duration of aRCC (month)	n	xxx
	Mean±SD	xx.xx±xx.xx
	Median	xx.xx
	Min~Max	xx.xx~xx.xx
	Category 1	xxx(xx.xx)
	Category 2	xxx(xx.xx)

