Footnote: Sub-group 1: Subjects who are first administered INLYTA® during the study period

Sub-group 2: Subjects who has continued administration of INLYTA® since the time prior to the contract date

Dummy Table

[Table 21] Adverse events by their other causality

System Organ Class [§] Preferred Term	Disease under the study	Number of adverse events by their other causality (%)		
		Other disease	Concomitant treatment drug or non-drug	Others
System Organ Class Preferred Term	xxx(xx.xx)	xxx(xx.xx)	xxx(xx.xx)	xxx(xx.xx)
	xxx(xx.xx)	xxx(xx.xx)	xxx(xx.xx)	xxx(xx.xx)
	xxx(xx.xx)	xxx(xx.xx)	xxx(xx.xx)	xxx(xx.xx)
Total	xxx(xx.xx)	xxx(xx.xx)	xxx(xx.xx)	xxx(xx.xx)
§MedDRA latest version				

Programming note: This table is repeated for each sub-group with the following table title and footnote.

Title : [Table 21-x] Adverse events by their other causality (sub-group x: N=xxx)

Footnote: Sub-group 1: Subjects who are first administered INLYTA® during the study period

Sub-group 2: Subjects who has continued administration of INLYTA® since the time prior to the contract date

[Table 22] Adverse events by action

System Organ Class [§] Preferred Term	Discontinuation	Number of adverse events by action (%)		
		Dosage reduced	Dosage increased	No change
System Organ Class Preferred Term	xxx(xx.xx)	xxx(xx.xx)	xxx(xx.xx)	xxx(xx.xx)
	xxx(xx.xx)	xxx(xx.xx)	xxx(xx.xx)	xxx(xx.xx)
	xxx(xx.xx)	xxx(xx.xx)	xxx(xx.xx)	xxx(xx.xx)
Total	xxx(xx.xx)	xxx(xx.xx)	xxx(xx.xx)	xxx(xx.xx)
§MedDRA latest version				

Programming note: This table is repeated for each sub-group with the following table title and footnote.

Title : [Table 22-x] Adverse events by action (sub-group x: N=xxx)

Footnote: Sub-group 1: Subjects who are first administered INLYTA® during the study period

Sub-group 2: Subjects who has continued administration of INLYTA® since the time prior to the contract date

Dummy Table

[Table 23] Occurrence status of adverse events by demographic characteristics

Factor	Classification	No. of Subjects	Incidence of AE n(%)	[95% CI]	p-value ¹⁾²⁾
Sex	Male	xxx	xxx(xx.xx)	[xx.xx, xx.xx]	x.xxxx
	Female	xxx	xxx(xx.xx)	[xx.xx, xx.xx]	
	Total	xxx	xxx(xx.xx)	-	
Age	Category 1	xxx	xxx(xx.xx)	[xx.xx, xx.xx]	x.xxxx
	Category 2	xxx	xxx(xx.xx)	[xx.xx, xx.xx]	
	Category 3	xxx	xxx(xx.xx)	[xx.xx, xx.xx]	
	...	xxx	xxx(xx.xx)	[xx.xx, xx.xx]	
Pediatric	Total	xxx	xxx(xx.xx)	-	
	< 19 years	xxx	xxx(xx.xx)	[xx.xx, xx.xx]	x.xxxx
	≥ 19 years	xxx	xxx(xx.xx)	[xx.xx, xx.xx]	
Geriatric	Total	xxx	xxx(xx.xx)	-	

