	≥ 65 years	xxx	xxx(xx.xx)	[xx.xx, xx.xx]	x.xxxx
	< 65 years	xxx	xxx(xx.xx)	[xx.xx, xx.xx]	
Classification	Total	xxx	xxx(xx.xx)	-	
	Outpatient	xxx	xxx(xx.xx)	[xx.xx, xx.xx]	x.xxxx
	Inpatient	xxx	xxx(xx.xx)	[xx.xx, xx.xx]	
	Total	xxx	xxx(xx.xx)	-	

¹⁾Chi-square Test

²⁾Fisher's Exact Test

*Statistically significant

Programming note: This table is repeated for each sub-group with the following table title and footnote.

Title : [Table 23-x] Occurrence status of adverse events by demographic characteristics (sub-group x: N=xxx)

Footnote: Sub-group 1: Subjects who are first administered INLYTA® during the study period

Sub-group 2: Subjects who has continued administration of INLYTA® since the time prior to the contract date

[Table 24] Occurrence status of adverse events by other baseline characteristics

Factor	Classification	No. of Subjects	Incidence of AE n(%)	[95% CI]	p-value ¹⁾²⁾
Duration of aRCC	Category 1	xxx	xxx(xx.xx)	[xx.xx, xx.xx]	x.xxxx
	Category 2	xxx	xxx(xx.xx)	[xx.xx, xx.xx]	
	Category 3	xxx	xxx(xx.xx)	[xx.xx, xx.xx]	
	...	xxx	xxx(xx.xx)	[xx.xx, xx.xx]	
	Total	xxx	xxx(xx.xx)	-	
Cell component of aRCC	Clear cell	xxx	xxx(xx.xx)	[xx.xx, xx.xx]	x.xxxx
	Other	xxx	xxx(xx.xx)	[xx.xx, xx.xx]	
	Total	xxx	xxx(xx.xx)	-	
Metastasis	Yes [§]	xxx	xxx(xx.xx)	[xx.xx, xx.xx]	x.xxxx
	Liver	xxx	xxx(xx.xx)	[xx.xx, xx.xx]	
	Lung	xxx	xxx(xx.xx)	[xx.xx, xx.xx]	
	Bone	xxx	xxx(xx.xx)	[xx.xx, xx.xx]	
	Brain	xxx	xxx(xx.xx)	[xx.xx, xx.xx]	
	Skin	xxx	xxx(xx.xx)	[xx.xx, xx.xx]	
	Lymph nodes	xxx	xxx(xx.xx)	[xx.xx, xx.xx]	
	Other	xxx	xxx(xx.xx)	[xx.xx, xx.xx]	
	No	xxx	xxx(xx.xx)	[xx.xx, xx.xx]	
	Total	xxx	xxx(xx.xx)	-	
Primary lesion surgery	Done	xxx	xxx(xx.xx)	[xx.xx, xx.xx]	x.xxxx
	Not done	xxx	xxx(xx.xx)	[xx.xx, xx.xx]	
	Total	xxx	xxx(xx.xx)	-	

Dummy Table

Factor	Classification	No. of Subjects	Incidence of AE n(%)	[95% CI]	p-value ¹⁾²⁾
	Total	xxx	xxx(xx.xx)	-	
Medical history	Yes	xxx	xxx(xx.xx)	[xx.xx, xx.xx]	x.xxxx
	No	xxx	xxx(xx.xx)	[xx.xx, xx.xx]	
	Total	xxx	xxx(xx.xx)	-	
Renal impairment	Yes	xxx	xxx(xx.xx)	[xx.xx, xx.xx]	x.xxxx
	No	xxx	xxx(xx.xx)	[xx.xx, xx.xx]	
	Total	xxx	xxx(xx.xx)	-	
Hepatic impairment	Yes	xxx	xxx(xx.xx)	[xx.xx, xx.xx]	x.xxxx
	No	xxx	xxx(xx.xx)	[xx.xx, xx.xx]	
	Total	xxx	xxx(xx.xx)	-	
Allergic history	Yes	xxx	xxx(xx.xx)	[xx.xx, xx.xx]	x.xxxx
	No	xxx	xxx(xx.xx)	[xx.xx, xx.xx]	
	Total	xxx	xxx(xx.xx)	-	
Prior chemotherapy	Yes	xxx	xxx(xx.xx)	[xx.xx, xx.xx]	x.xxxx
	No	xxx	xxx(xx.xx)	[xx.xx, xx.xx]	
	Unknown	xxx	xxx(xx.xx)	[xx.xx, xx.xx]	

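### Up to 114 one-factor tests are each run at an unadjusted 5% level and marked statistically significant, with no multiplicity control and no exploratory label

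*SAP*

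**What the plan says.** SAP 5.1 sets one rule for all testing: "two-sided tests will be conducted at a 5% significance level and the p-value of each test result will be presented in the summary table".

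SAP 6.2(3) states the aim of the adverse-event screen: "To identify statistically significant difference in incidence of adverse events by categorical variables of demographic and other baseline characteristics". SAP 6.3(4) states the parallel aim for response: "To identify statistically significant difference in objective response rate by categorical variables of demographic and other baseline characteristics". In both places the chi-square test, or Fisher's exact test when expected counts are small, is prescribed and not left optional.

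The dummy tables fix the number of tests. Table 23 has 5 p-values (sex, age category, pediatric, geriatric, inpatient/outpatient) and Table 24 has 14. Tables 29 and 30 repeat the same 5 and 14 for objective response. All four carry an asterisk footnote reading "Statistically significant", and each is repeated for both sub-groups, as SAP 6.4 requires.

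Neither document mentions a multiplicity adjustment, false-discovery control or an exploratory label for these tests. The protocol is softer: section 3.9 describes the evaluation as mainly summary displays, and 3.9.1 presents the sub-group tests as something that may be done if required.

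**The concern.** A screen of many factors at 5% each will often flag something by chance. Here the flag is an asterisk that declares statistical significance, and the stated purpose of the tests is to find such differences. The tables go into a regulatory re-examination report. Its reader gets no warning that the asterisks are unadjusted, and could take a chance association between, say, allergic history and adverse events as a finding. What is at stake is which factors the report declares significant. The incidence and response estimates themselves are not affected.

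**Working it through.** The plan gives no test count, family-wise error rate or power calculation, so there is no stated figure to reproduce. The minimum of 100 subjects in SAP 2.4 is a regulatory number.

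**Count of tests (from the dummy tables)**
- Factors per outcome: 5 + 14 = 19.
- Two outcomes: 19 × 2 = 38 tests in all subjects.
- Three populations (all subjects, sub-groups 1 and 2): 38 × 3 = 114.
- The exclusion criteria bar patients under 18, so the pediatric (<19 years) row can hold only 18-year-olds. If none enrols, 1 × 2 × 3 = 6 tests drop out and 114 − 6 = 108 remain.
- Duration of administration and daily average dose are known only after treatment starts. They account for 2 × 2 × 3 = 12 tests, where an association may be structural and not due to chance.
- Leaving out the pediatric row and these two: 19 − 1 − 2 = 16 factors per outcome.

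**Nominal error, if every test had exactly 5% and were independent**
- Expected false asterisks: 114 × 0.05 = 5.7; all-subjects tables only, 38 × 0.05 = 1.9.
- At least one false asterisk in 16 tests: 1 − 0.95^16 = 0.56.

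These are upper-end figures, because Fisher's test is conservative and the total population contains both sub-groups.

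**Allowing for the actual test rule**

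A simulation used the SAP's chi-square/Fisher rule with 100 subjects and 16 independent binary factors of prevalence 10–70%, none related to the outcome. The documents give no adverse-event incidence or response rate, so a range is shown.

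| Assumed outcome rate | P(at least one false asterisk), all subjects, one outcome |
|---|---|
| 20% or 80% | about 50% |
| 90% | about 40% |
| 95% | about 26% (26–28% between runs) |

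Both outcomes together, treated as independent, with response at 20%:
- adverse-event incidence 80%: 1 − 0.50 × 0.50 = 0.75
- 90%: 1 − 0.50 × 0.60 = 0.70
- 95%: 1 − 0.50 × 0.74 = 0.63

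**Adding the sub-group repeats**

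A wider simulation took 18 binary factors (the pediatric row left out), two equal sub-groups, 100 or 150 subjects, adverse-event incidence 70–97% and response 20–30%. It gave about 2.3–4.9 false asterisks per full set of tables, and at least one in about 82–99% of sets.

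**After the fix**

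With the Benjamini-Hochberg adjustment within each outcome, the first simulation gives any false asterisk in about 1–5% of total-population sets. A lone true factor among 19 would need a raw p-value of about 0.05/19 = 0.0026 to keep its asterisk.

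**The case against.** The strongest reply is that no error rate is being spent. The study has no hypothesis, comparator, primary test or stopping rule; its objective is to monitor use. Unadjusted screening is a defensible choice in such a study, safety screening should be sensitive, and every row already shows a count, a rate and usually a 95% interval. Protocol 3.12 adds that the SAP follows the regulator's post-marketing guideline. This stands as far as it goes. It argues for keeping the tests and raw p-values, and it limits the point to labelling. It does not justify an unqualified significance mark, which goes further than the optional, descriptive testing in protocol 3.9.1.

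Some stronger readings are tempting but unsupported:
- **The tests are repeated at every periodic report.** Protocol 3.9.2 says "Interim analysis will be performed in time for the report submission", and these four tables lack the note that confines Tables 10, 12, 14, 25 and 31 to the re-examination report. Recurrence is therefore plausible. But no text says so for these tables, and SAP 5.1 places analysis after database lock. It remains an inference, and no repeated-look error rate is claimed.
- **About 5.7 false asterisks should be expected.** This ignores overlap, conservatism, the near-empty pediatric row and the exposure factors.
- **Data-driven cut-points make it worse.** Table 1 notes "The categories of age will be set considering distribution of data". Cuts made on a factor's own distribution, without regard to the outcome, do not inflate type I error.
- **The pediatric row should go.** SAP 3.3 ties the special populations to regulatory guidelines, and a near-empty row does little harm.
- **Chance factors will be reported as safety signals.** The SAP does not use that term here. It leaves the question of which factors affect safety or efficacy to the regressions.

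**Conclusion.** The point holds as a labelling fault that is cheap to correct. The plan prescribes up to 114 unadjusted 5% tests (about 108 if no 18-year-old enrols) and stamps the hits as significant without qualification. With no real effects, a false asterisk in the total-population tables is more likely than not over the two outcomes together: about 63–75% under the stated assumptions. It is not always more likely than not for one outcome alone, where it falls to about 26% at a rate of 95%. These figures rest on assumed rates and on independent binary factors. Some real factors overlap (age category and geriatric) or have more than two levels. The main estimates and intervals are unaffected, and no confirmatory claim is at risk.

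**What to change.** In SAP 5.1, 6.2(3), 6.3(4) and 6.4, and in the footnotes to Tables 23, 24, 29 and 30:
- Keep all incidences, response rates, 95% intervals and raw p-values, in every population, and footnote the p-values as unadjusted and exploratory.
- Print the significance asterisk only in the total-population tables, and only where the Benjamini-Hochberg adjusted p-value is below 0.05. Take the adjustment over all factors tested for that outcome: Tables 23 and 24 together, and Tables 29 and 30 together.
- Print no asterisk in the sub-group repeats, or in any periodic report that includes these tables.

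The cost is some SAP wording and a few lines of programming. No data collection or site work changes. The downside is fewer flagged factors, since a lone true factor needs a raw p-value of about 0.0026. Because the raw p-values and intervals stay visible, a reader who wants a more sensitive screen loses nothing.

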5.2. Handling of Missing and Incomplete data

5.2.1. Handling of Missing data

If data are missing or if a subject decides to discontinue from the study, there will be no imputation applied except as specified in section 5.2.2. The impact of missing data will be evaluated as appropriate.

5.2.2. Handling of Missing and Incomplete dates

Missing or incomplete dates will be handled by following rule:

	Missing	Imputation
Date of initial diagnosis	DD	01
	MM/DD	01/01
	YYYY/MM/DD	No imputation
End date of administration for study drug	'Ongoing'	Date of final follow-up

6. Statistical Analyses

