6.1.2. Diagnosis of advanced renal cell carcinoma (aRCC)

- 1) Duration of aRCC (month) will be presented in n, mean, SD, median, minimum and maximum. Also, frequency and percentage of each group categorized according to the distribution of duration of aRCC will be presented.

Duration of aRCC (month)

$$= \frac{(Start\ date\ of\ first\ administration) - (Date\ of\ initial\ diagnosis) + 1}{30.4375}$$

- 2) Cell component of aRCC will be presented in frequency and percentage.
- 3) Metastasis will be presented in frequency and percentage. In case of 'yes', categorized metastasis site will be presented in frequency and percentage.
- 4) Primary lesion surgery will be presented in frequency and percentage.

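### Partial diagnosis dates are set to the earliest possible day, so duration of aRCC can only be lengthened: by about 6 months on average for year-only dates, if true dates are uniform

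*SAP*

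**What the plan says.** SAP 5.2.1 limits imputation to one place: "there will be no imputation applied except as specified in section 5.2.2". SAP 5.2.2 opens with "Missing or incomplete dates will be handled by following rule" and then gives the rule for the date of initial diagnosis. A missing day is set to 01, a missing month and day are set to 01/01, and a wholly missing date is left missing. No reason is given for choosing the start of the period. There is no sensitivity analysis for these dates beyond a general promise in 5.2.1 to look at the effect of missing data.

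SAP 6.1.2 uses the date in one derived variable: (start of first administration − date of initial diagnosis + 1) / 30.4375. It is summarised as a continuous variable: "Duration of aRCC (month) will be presented in n, mean, SD, median, minimum and maximum". It is also grouped from the data: "frequency and percentage of each group categorized according to the distribution of duration of aRCC will be presented".

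The grouped variable is then tested. "Duration of aRCC" is the first factor in dummy Table 24 (AE incidence) and dummy Table 30 (objective response), each with a p-value column. The tests come from SAP 6.2 item 3 ("To identify statistically significant difference in incidence of adverse events by categorical variables of demographic and other baseline characteristics") and SAP 6.3 item 4 ("To identify statistically significant difference in objective response rate by categorical variables of demographic and other baseline characteristics"). SAP 5.1 sets the level: "two-sided tests will be conducted at a 5% significance level". SAP 6.4 repeats both analyses in each of the two sub-groups.

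**The concern.** An imputation rule that always picks the earliest admissible date makes errors in one direction only. First dose is fixed and diagnosis is moved back, so the interval between them grows or stays the same. Errors across subjects add up instead of cancelling.

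Two results are exposed. One is the reported disease duration, which describes who was treated. The other is the grouping used in Tables 24 and 30, where subjects with partial dates can land in a longer-duration category than they belong to. As a baseline characteristic, duration is also eligible for the logistic regressions in SAP 6.2 item 4 and 6.3 item 5, although dummy Tables 25 and 31 name no specific factors.

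Partial dates are foreseeable: the SAP provides for them, the study has a retrospective component (Protocol 3.1), and data on patients already taking INLYTA are gathered only so far as possible (Protocol 3.5.4).

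**Working it through.** The plan states no figure for the shift, so there is none to reproduce.

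**Inputs.** The imputation rule is from SAP 5.2.2. The duration formula and the divisor 30.4375 are from SAP 6.1.2. Assumption: the true diagnosis date is uniform over the unknown part of the date.

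**Formula.** First dose and the +1 cancel, so

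lengthening (months) = (true diagnosis date − imputed date) / 30.4375.

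**Year-only dates, set to 01/01.** The difference runs from 0 to 364 days (0 to 365 in a leap year).
- 365-day year: mean 364/2 = 182.0 days; 182.0/30.4375 = 5.98 months.
- Leap year: mean 365/2 = 182.5 days; 182.5/30.4375 = 6.00 months.
- Range 0 to about 12 months, standard deviation about 3.5 months.

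**Only the day missing, set to 01.** Averaged over every calendar day, the mean is 14.7 to 14.8 days, or 0.48 month (maximum 0.99 month).

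**Check with the full formula.** For diagnoses spread over 2015 and first dose on 15 June 2018 (an illustrative date), mean true duration is 35.48 months and imputed duration is 41.46 months. The difference is 5.98.

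**Year-only, with first dose in the same calendar year.** The true date cannot fall after first dose, so the shift is smaller.
- First dose uniform over the year and diagnosis uniform before it: 182/2 = 91 days = 2.99 months.
- Both uniform, restricted to diagnosis on or before first dose: 364/3 = 121.3 days = 3.99 months.

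**Effect on the cohort mean.** This is share of year-only dates × 5.98 months. The documents give no share, so these are assumptions only:

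| Assumed share year-only | Rise in cohort mean (months) |
|---|---|
| 2% | 0.12 |
| 5% | 0.30 |
| 10% | 0.60 |
| 20% | 1.20 |
| 30% | 1.79 |

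**Effect on categories.** The SAP fixes no cut points. With assumed fixed widths of 6, 12 or 24 months, about 75%, 50% or 25% of year-only subjects would move up at least one category.

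**Midpoint rule, before any cap.**
- 1 July for year-only dates: mean error +0.02 to +0.03 month, range about −6.0 to +6.0.
- Day 15 for day-missing dates: mean error +0.02 month, range −0.46 to +0.53.

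**Midpoint rule capped at first dose, same calendar year.** Count days from 1 January, so 1 July is day 181, and set the imputed day to the smaller of 181 and the first-dose day.
- First-dose day uniform on 0 to 364: mean imputed day = (181×182/2 + 181×183)/365 = 135.9, against a mean true day of 91. Error −44.9 days = −1.5 months, compared with +3.0 under the present rule.
- Both uniform, restricted: mean imputed day 166.0 (the same minimum, weighted by first-dose day + 1), against 121.3. Error −44.6 days = −1.5 months, compared with +4.0.

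So the capped midpoint is not exact here, but its average error is smaller.

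**The case against.** The best defence is that first-of-period imputation is a transparent, pre-specified convention that contradicts nothing else in the documents. It also has a practical merit: the imputed date can never fall after the true one, so it cannot place diagnosis after first dose. An uncapped 1 July rule can. That merit is real, but a cap secures it too, using dates the study already collects (Protocol 3.5.4.6 and 3.5.4.8). Being a convention does not remove the one-sided error.

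Several other points stand and limit the finding:
- The cap needs a fallback. SAP 5.2.2 has no rule for partial prior-therapy dates, and 5.2.1 allows no other imputation.
- The 6.0 months applies only to year-only dates and rests on uniformity. Required failure of one prior systemic therapy makes diagnosis and first dose in the same year less likely, but does not exclude it.
- Midpoint imputation still leaves a year-only date wrong by up to about 6 months either way.
- The study is descriptive surveillance with a regulatory minimum of 100 subjects and no powered hypothesis. Duration is one of many exploratory factors.

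Stronger readings are tempting, and the documents do not support them:
- **A definite overstatement of cohort duration.** The share of partial dates is not stated, and with few such dates the median need not move.
- **Partial dates belong to patients with older diagnoses or diagnosed elsewhere.** Nothing in either document says so.
- **The p-values in Tables 24 and 30 are distorted by a known amount.** With data-driven categories and an unknown share, no effect on a p-value or odds ratio can be derived.
- **The MSKCC and Heng factors are affected.** The site records the factor for under one year from diagnosis to first systemic therapy (Protocol 3.5.4.4). The SAP does not derive it from the imputed date.

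**Conclusion.** The point holds as a minor one. The rule in SAP 5.2.2 can only lengthen duration of aRCC for subjects with a partial diagnosis date. Under uniform true dates, the mean shift is about 6.0 months for year-only dates, about 3 to 4 months if first dose is in the same calendar year, and about 0.5 month when only the day is missing. An individual error can be zero; the average error cannot be negative.

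The consequence for the cohort mean and for Tables 24 and 30 remains undetermined until the number of partial dates is known. The tabulated shares and category widths are illustrations, not estimates. ORR, PFS, TTP and overall AE incidence are unaffected, so no main result of the study depends on this.

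**What to change.** In the diagnosis-date row of SAP 5.2.2:
- impute day 15 when only the day is missing, and 1 July when month and day are missing;
- if that date falls after the start of first prior systemic therapy, use the therapy start date, provided it is complete; if it is not complete, cap at the first INLYTA dose instead;
- leave a wholly missing date unimputed, as now.

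Report the number of imputed dates, separately for day-missing and year-only, beside the duration summary. Readers can then judge how much the change matters.

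The cost is one amended row and one extra capping rule. No new data are needed, and neither sample size nor endpoints change. The remaining limitation is that the midpoint centres the average error but does not put each subject in the right category, and where the cap applies the error is reduced, not removed.
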